8.0 Study Endpoints

8.1 Primary Endpoints

Phase 1:

o The safety will be determined by recording the occurrence of AE during the first 30 days post final I-PDT day, using the revised NCI Common Terminology Criteria for Adverse Events (CTCAE) version 5.0.

Exploratory Endpoint

Objective target tumor response rates will be assessed according to RECIST v1.1 at 12 ± 2 weeks post I-PDT as described in section 16.2.

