10.2 Interstitial Photodynamic Therapy (I-PDT)

10.2.1 Porfimer Sodium Administration

Subjects will receive a single intravenous dose of porfimer sodium that will be administered approximately 48 ± 8 hours before the first I-PDT treatment.

Drug administration will take place in a room that has covered windows to protect the subjects from light exposure that can induce phototoxicity (i.e., direct sun light or visible artificial light that is more than 60 W). The Principal Investigator or designee will inject the subjects with porfimer sodium for this study.

A dose of 2 mg/kg of porfimer sodium will be administered by slow intravenous injection into a vein (3-5 minutes). Light-avoidance measures for approximately 30-90 days will be required. The Clinical Research Coordinator and staff nurses will explain the light-avoidance measures to each subject and written instructions will be handed out to the subjects (**Appendix F**). The subject will be cautioned to protect the site of the infusion from excessive direct sunlight and certain bright lights for up to 3 months. The site may be exposed to normal ambient light.

Vital signs will be done immediately after the end of the injection and 15 minutes after.

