10.3 Definition of Dose-Limiting Toxicity

Dose Limiting Toxicities will include:

Any adverse events (AEs) that are \geq grade 4 that are possibly, probably, or definitely related to the I-PDT, by recording the occurrence of AE during the first 30 days post final I-PDT treatment using the revised the National Cancer Institute (NCI) Common Terminology Criteria for Adverse Events version 5.0 (CTCAE v5.0). Dose Limiting Toxicities will be evaluated for 30 days post final I-PDT day.

If participants experience DLTs, further I-PDT sessions will be held until DLT resolution as well as after porfimer sodium clearance.

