13.0 Risks to Subjects

This is a Greater Than Minimal Risk study according to IRB criteria. Phototoxicity is the most likely potential risk associated with the systemic administration of the porfimer sodium. Proper shielding from the procedure room lights will be maintained and the pulse oximetry sensor will be rotated every 15 minutes, to minimize this risk. The subjects will be provided with written instructions on how to protect themselves from excessive light exposure.

The site-specific toxicity associated with this therapy includes:

- a. **Injection site reaction:** Very common effects include pain at the injection site (12%) which is transient and can be minimized by slowing the injection rate. Common effects include injection site reaction (3%) and burning sensation (3%).
- b. **Tumor/local tissue reaction:** Very common effects include pain (15%), hemorrhage (15%) and scaring (12%). Common effects include edema (8%), localized infection (8%), fever (8%), and skin necrosis (2%).
- c. **Phototoxicity:** Common effects include sunburn (3%), blisters (5%), erythema (5%), hyper-pigmentation (3%), and cutaneous photosensitivity (3%).
- d. **Other systemic events:** Constipation (11%), vomiting (9%), anemia (8%), nausea (6%) and giddiness (2%).
- e. Collection of blood: Potential rare risks include local bleeding, inflammation and infection at the collection site (<1% of patients).

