17.3 Reporting Adverse Events

Routine AEs occurring between the start date of intervention until 30 days after the last intervention, or until the event has resolved, the study participant is lost to follow-up, the start of a new treatment, or until the study investigator assesses the event(s) as stable or irreversible, will be reported. New information will be reported after it is received.

Table 1 Guidelines for Routine Adverse Event Reporting for Phase 1 Studies (Regardless of Expectedness)

Attribution	Grade 1	Grade 2	Grade 3	Grade 4
Unrelated	X	X	X	X
Unlikely	X	X	X	X
Possible	X	X	X	X
Probable	X	X	X	X
Definite	X	X	X	X

Routine AEs occurring between the start of intervention until 30 days after the last intervention or until the event has resolved, stabilized, death, or a new treatment is started, whichever comes first, will be reported. New information will be reported after it is received.

Pinnacle Biologics, Inc. Bannockburn IL, will be receiving copies of all the reports (de-identified).

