9. You must report any redness, swelling, tenderness, blistering, sunburn, or any

other event that does not usually happen to you.

10. Remember that your doctor is here to study the usefulness of Photofrin®

and photodynamic therapy for the treatment of tumors; your questions,

concerns, and symptoms are important.

11. Please help the doctor to learn more about you and your treatment by

keeping lists of questions, concerns, and symptoms. Your doctor will

address these when you see them. Also, remember that the nurse can aid

you at any time.

12. You are welcome to bring any family member or close friend to your

appointments to help you in communicating with your doctor.

Skin Testing After Photofrin®

1. When should I test my skin?

Approximately 1 month after receiving the drug Photofrin®.

2. What do I do?

Cut a hole in a paper bag approximately 2-inch diameter. Place the bag over your forearm. Cover all other skin thoroughly. Expose the 2-inch diameter of the forearm skin to direct sunlight for one minute, then examine for evidence of skin reaction, such as redness, blistering or burning sensation. If there is no reaction, expose the skin again, and check it in another minute. Repeat this procedure up to eight more times, provided there is no sign of skin reaction.

3. What if I see a skin reaction?

Immediately cover the exposed skin and stop the skin test. You may retry skin testing in a few days. Contact your doctor or nurse to find out more information.

4. What if I don't have a skin reaction?

If there is no reaction after the above procedure, cover the exposed skin and protect yourself from sunlight for 24 hours. Re-examine the exposed skin at the end of this time. If there is no delayed skin reaction, slowly begin to increase your time in direct light.

5. Should I use sunscreen?

No. A sunscreen will not help protect your skin from the sun when using Photofrin®.

Appendix G Tumor response following irRECIST, according to attachment: "irRECIST-path-PDF Bohnsack et al 2014 ESMO abstract.pdf".

Target Lesion Selection for irRECIST

• Follow the definitions from RECIST 1.1

Non-measurable Lesion Definitions for irRECIST

• Follow the definitions from RECIST 1.1

Response	Criteria for Response per irRECIST
Complete Response (irCR)	irCR : complete disappearance of all measurable and non-measurable lesions. Lymph nodes must decrease to < 10 mm in short axis. Confirmation of response is not mandatory.

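### Late-onset, non-serious phototoxicity is not systematically captured: routine AE reporting closes about day 32 after the drug, while light precautions can run to day 90

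*Combined protocol and SAP*

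**What the plan says.** **Risk period.** Section 13.0 states: "Phototoxicity is the most likely potential risk associated with the systemic administration of the porfimer sodium". Section 10.2.1 adds: "Light-avoidance measures for approximately 30-90 days will be required". It also asks that the infusion site be protected from "excessive direct sunlight and certain bright lights for up to 3 months". The patient instruction sheet (Appendix F) gives the time for a direct-sunlight skin test as "Approximately 1 month after receiving the drug Photofrin". A patient who reacts covers up and may retry after a few days. One who does not react builds up sun exposure gradually.

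**AE collection.** The primary safety endpoint in 8.1 rests on "recording the occurrence of AE during the first 30 days post final I-PDT day". Section 10.3 uses the same period: "Dose Limiting Toxicities will be evaluated for 30 days post final I-PDT day". Section 17.3 reports "Routine AEs occurring between the start of intervention until 30 days after the last intervention", and in its second statement the start of a new treatment is one of the events that closes reporting early. In Appendix D the adverse-event row is marked up to the 30-day visit and is blank under Follow-Up. The Appendix D1 row is also blank there.

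**Other provisions.** Section 17.4.1 keeps SAEs reportable after 30 days when they are judged at least possibly related. Section 11.6 schedules safety evaluations every 1-3 months in year 1. Section 19.6 tabulates toxicities by grade.

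**A different anchor.** Section 19.3 counts its SAE window from the first SOC treatment, or from the last I-PDT if no SOC is given. Appendix D note 13 and Appendix D1 note M set AE reporting at 30 ± 2 days after first SOC treatment.

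**The concern.** Safety is the primary objective, and phototoxicity is the risk the protocol itself ranks as most likely. Routine AE reporting closes at about the time patients start planned sunlight exposure, and possibly well before light precautions end. A mild or moderate burn or blister beginning in that interval would follow the protocol's own instructions on exposure, yet nothing schedules its entry on an AE form. The grade table in 19.6 could then understate low-grade phototoxicity, and a reader of the results could not tell whether late events were absent or simply not recorded.

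The conflicting anchors add to this. Under 17.3 the start of a new treatment can end AE reporting; under the Appendix D notes the start of SOC begins the 30-day count. Two data managers could collect different AEs from the same patient and both be following the document.

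**Working it through.** The plan gives no figure for this, so the check is a day count followed by a rough scale.

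**Inputs.**
- Drug to first light: "administered approximately 48 ± 8 hours before the first I-PDT treatment", that is 40-56 h or 1.7-2.3 days (10.2.1).
- Routine AE window: 30 days after the last intervention (17.3).
- Light precautions: about 30-90 days (10.2.1).
- Added light without new drug: sessions within 14 days of the first (Appendix D note 16), or light-only treatment within 2-3 weeks of the drug (note 17).
- Phototoxicity rates: sunburn 3%, blisters 5%, erythema 5%, hyperpigmentation 3%, cutaneous photosensitivity 3%, with no onset times (13.0).
- Maximum sample size: 12 (4.0).

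**Step 1: day the window closes, counted from the drug.** Close = (days from drug to last light) + 30. Uncovered = 90 - close.

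| Case | Close | Uncovered of 90 days |
|---|---|---|
| Single session at 48 h | 2 + 30 = day 32 | 58 (64%) |
| Further session 14 days after the first | 16 + 30 = day 46 | 44 (49%) |
| Light-only treatment at 3 weeks | 21 + 30 = day 51 | 39 (43%) |
| Precautions needed for 30 days only | day 32 | 0 (0%) |

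The ± 8 h moves the first row only between day 31.7 and day 32.3. With repeat courses of drug plus light, earlier doses are partly or fully covered, but the period after the last dose has the same gap.

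**Step 2: effect of the anchor.** Under the Appendix D notes, if SOC started 30 days after I-PDT (an assumption, since no date is fixed), the window would close at 2 + 30 + 30 = day 62, leaving 28 of 90 days (31%). Under the new-treatment clause in 17.3, SOC starting before day 30 would close it earlier than day 32.

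**Step 3: scale in patients.** For a 5% event over the whole period, the expected count is 12 × 0.05 = 0.6 and the chance of at least one is 1 - 0.95^12 = 46%. The documents do not say what share begins late. Assuming 10-50%:
- per 5% term: 12 × 0.05 × 0.10 = 0.06 to 12 × 0.05 × 0.50 = 0.30 cases outside the window. The chance of at least one is 1 - 0.995^12 = 6% to 1 - 0.975^12 = 26%.
- all five terms, if they never overlap (3 + 5 + 5 + 3 + 3 = 19%): 12 × 0.19 × 0.10 = 0.23 to 12 × 0.19 × 0.50 = 1.14 cases.

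**Step 4: effect of the fix on the window.** Day 90 after the drug is about day 88 after I-PDT, so the targeted collection adds about 58 days to the present 30. The sample size does not change.

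**The case against.** A reader might infer that late phototoxicity is missed altogether. The documents do not support that. Related SAEs stay reportable without a time limit, safety evaluations continue through year 1, and the patient sheet tells patients to report redness, blistering or sunburn with no end date. The first paragraph of 17.3 can also be read as following an event that began inside the window until it resolves. A reaction to a skin test near one month may be picked up at the 30-day visit, where AEs are recorded. All of this stands, and it confines the gap to non-serious events with onset after the cut-off. It does not close the gap, because the later visits and the patients' reports have no AE recording attached to them.

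A second tempting inference is that 64% of phototoxic events are lost. That figure is calendar time for a single session at the upper end of the stated range. The rates in 13.0 carry no onset times, so they do not show how many events, if any, begin after day 32.

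It can also be said that nothing decisive depends on this. The porfimer dose is fixed, only the fluence rate changes between levels, and DLTs are related events of grade 4 or higher within 30 days. Late low-grade skin events cannot alter the recommended irradiance. That is correct, and it limits the importance of the point. But the primary objective is the safety of porfimer-mediated I-PDT as a whole, and 19.6 reports all grades.

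Finally, the SOC-anchored notes could lengthen the window. They could, but they conflict with 17.3, so the protocol cannot rely on them as written.

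**Conclusion.** The point holds in this limited form: late-onset, non-serious phototoxicity is not systematically captured, and the passages defining the AE window contradict one another. For a single session under 17.3, reporting ends about day 32 after the drug. The uncovered share of a 90-day period is up to 64% of calendar time, about 43-49% with added light-only sessions, and 0% if sensitivity lasts 30 days. Expected numbers are small: 0.06-0.30 cases per 5% term among 12 patients, on the assumed 10-50% late share.

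The conclusion assumes that 17.3 governs onset of new events and that the blank Follow-Up cells mean no AE recording is planned there. Only items 9 onward of the numbered patient instructions could be read, and the point does not depend on the earlier items. Dose decisions and sample size are unaffected. It is a matter of completeness in the safety description, and worth correcting because the correction is cheap.

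**What to change.** 1. Keep the 30-day DLT window in 10.3 as it is.
2. Reconcile 8.1, 17.3, 19.3, Appendix D note 13 and Appendix D1 note M to one anchor for AE reporting, and state whether the start of SOC ends the window, starts it, or does neither.
3. In 17.3, 19.6 and the Follow-Up column of the adverse-event rows in Appendix D and D1, add recording of skin and photosensitivity AEs of any grade until 90 days after the last porfimer dose, including after SOC starts. Use the existing 1-3 monthly visits or a telephone call. The call matters because a 3-month interval could leave only one visit before day 90, and Appendix D note 15 already accepts the telephone for quality of life.
4. Say in 8.1 and 19.3 that these later events are tabulated as a separate descriptive item alongside the 30-day primary safety endpoint, with onset day counted from the last porfimer dose.

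The cost is a small amount of extra recording for one class of AE in at most 12 patients, with no added visits. No change to the light-avoidance or re-exposure instructions is proposed.

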10.2.2 Pre-treatment Planning

For all participants receiving I-PDT, a standard diagnostic head and neck scan with CT or MRI, will be obtained within 4 weeks prior to I-PDT. This imaging will be used for pre-treatment planning that will be conducted at [name] laboratory at Roswell Park, with the treating physician at each participating site.

The pretreatment planning will be carried out by following these steps:

- 1. If possible, clinically approved surface fiducial markers (using removal stickers) will be affixed to the skin (at the region of the tumor) prior to CT or MRI, to assist in the guidance of laser fibers, as described in Oakley et al. 2017(40).
- 2. The scans will be de-identified, linked to a subject ID, and copied on CD or transferred via secure network to [name] laboratory, 5-14 business days prior to the scheduled I-PDT.
- 3. The treating physician will use the CT or MRI scans and the image reconstruction model for defining the clinical target volume (CTV).
- 4. Image analysis software will be used to reconstruct the CT or MRI scans to generate a computer model of tumors and adjacent anatomy as we described in Oakley et al. 2015 and Oakley et al. 2017.(40, 41)
- 5. The treating physician will also use the computer model to recommend the number and location of closed-end transparent catheters that can be safely placed within the CTV.

- 6. The computer model (of the CTV) will be imported into a finite element modeling (FEM) software, to calculate the light intensity (mW/cm) and energy (J/cm) that will be required to be delivered by each fiber, so that 100% of the CTV receives the target light dose (i.e. computed fluence rate >8.6 mW/cm² and fluence >45 J/cm²) as much as possible.
- 7. The FEM simulations will be presented to the treating physician for approval of the treatment plan at least 5 business days prior to the I-PDT.

Note: If subjects are scheduled to receive additional I-PDT courses (at least 30 days from the previous I-PDT, see Section 10.4), per the physician's discretion, pre-treatment planning procedures for additional I-PDT courses are per the physician's discretion.

10.2.3 I-PDT Procedure

The I-PDT will commence by following these steps:

- 1. An ultrasound system will be used, prior to fiber insertion, to confirm that the close-end sterile catheters can be safely placed into the CTV, according to the approved treatment plan. These catheters will be used to accommodate cylindrical laser fibers that will deliver the therapeutic light. If possible, an intraoperative CT (or other clinically approved radiological imaging) will be used to image the actual location of the inserted catheters.
- 2. Laser fibers with cylindrical end will be inserted into the close-end sterile catheters, according to the approved treatment plan. Only one laser fiber will be inserted into each catheter.
- 3. Additionally, dosimetry fibers to measure light will be inserted into other, nearby, close-end sterile catheters to monitor the light delivery.
- 4. The laser system(s) will be turned on to deliver the therapeutic light (630 ± 3 nm) into the tumor.
- 5. A light dosimetry system (described in Section 32.2) will be used to monitor the light fluence rate, fluence and tumor during I-PDT, in all participating sites.

The laser treatment and dosimetry fibers could be moved from one close-end sterile catheter to another to deliver the planned light fluence rate and fluence, and monitor the light and thermal dose. At any given time, there will be only one fiber (treatment or dosimetry) in a close-end sterile catheter. The laser fibers and detectors will not be in direct contact with patient tissue. Following administration of the laser light, the laser fibers and detectors will be removed, they will be cleaned and disinfected with an acceptable method (e.g., Cidex). The fibers and detectors can be reused, as they must be checked for calibration prior to each procedure.

Light Exposure Precautions

Light precautions will be maintained from the moment the subject enters the hospital and will continue while the subject is in the surgical suite and on the surgical subject care units.

Subjects are instructed to wear their protective eyewear when they travel to the hospital. The surgery will be performed with room lights, which are modified by amber filters to minimize unwanted activation of the photosensitizing drug and inadvertent light exposure to the subjects. Yellow filter paper will be employed over the procedure room lights and the surgeons' headlights

that blocks wavelength below 550 nm, thereby eliminating the light absorption by porphyrin in the UV and blue-green range.

It has been the experience thus far that the surgeons have been able to adapt safely to operating with such filters in place. Incisions, if needed, will be shielded from inadvertent light exposure with sterile blue towels sewn or secured to the skin edges. The remainder of the subject's skin will be draped in the usual surgical/sterile manner and therefore will not be inadvertently exposed to light during the entire procedure. The pulse-oximeter will be rotated between fingers every 15 minutes to avoid nail bed burns. Either disposable clips will be placed on all fingers, and the pulse-oximeter probe will be rotated or non-disposable clips will be rotated by the anesthesiologist.

These light precautions will be maintained throughout the entire hospital stay. Light precaution signs will be displayed above the subject's bed at all times.

Appropriate goggles will be furnished and available for the surgeons and others to operate and function in the operating room when the laser light is on.

10.3 Definition of Dose-Limiting Toxicity

Dose Limiting Toxicities will include:

Any adverse events (AEs) that are \geq grade 4 that are possibly, probably, or definitely related to the I-PDT, by recording the occurrence of AE during the first 30 days post final I-PDT treatment using the revised the National Cancer Institute (NCI) Common Terminology Criteria for Adverse Events version 5.0 (CTCAE v5.0). Dose Limiting Toxicities will be evaluated for 30 days post final I-PDT day.

If participants experience DLTs, further I-PDT sessions will be held until DLT resolution as well as after porfimer sodium clearance.

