10.4 Dose Escalation/Finding Schema

The FDA approved porfimer sodium dose (2 mg/kg) will not change. We will aim to deliver light fluence rate of ≥ 8.6 mW/cm² and fluence of ≥ 45 J/cm² to 100% of the CTV (dose level 1), as much as possible. Dose level -1 will ≥ 5.0 mW/cm² and fluence of ≥ 45 J/cm² to 100% of the CTV.

Table 2. The study plan for finding optimal fluence rate in I-PDT with Photofrin in patients with LAHNC.			
Dose Level Number of patients with DLT at a given dose level		Decision rules	
Dose Level 1 (Starting): The maximum fluence rate, scaled for	0 out of 3	Enter 3 patients at Dose Level 1 : The laser fluence rate and fluence, scaled for human, which induced maximum photoreaction in the animal models	
human, which induced effective	1 out of 3	Enter 3 more patients at this Dose Level .	

photoreaction in the animal models.	≥2	Enter 3 patients at Dose Level -1 : The laser fluence rate and fluence, scaled for human, which induced minimal toxicity in the animal models.
	≤ 1 out of 6	This is generally the recommended Phase II dose rate/dose. At least 6 patients must be entered at the recommended Phase II dose.

In participants where their tumors may require more than one course of I-PDT for complete effective illumination of the CTV, up to three sessions of I-PDT may be performed, at the discretion of the treating physician. The FDA approves to administer up to three courses of PDT with Photofrin® each separated by at least 30 days in the treatment of esophageal and endobronchial cancer (http://www.photofrin.com/wp-content/uploads/2013/02/prescribing-info.pdf.). Therefore, treatment sessions in this study will be conducted at least 30-days apart. The porfimer sodium dose (2 mg/kg) will remain the same.

See Appendix D 1 for the Dose Escalation Schedule of Events. The date of the last I-PDT course will be used to determine the scheduling of the follow up SoC related to this study.

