10.5 Treatment Discontinuation

All subjects who discontinue due to an AE must be followed until the event resolves or stabilizes. Appropriate medical care should be provided until signs and symptoms have abated, stabilized, or until abnormal laboratory findings have returned to acceptable or pre-study limits. The final status of the AE will be reported in the subject's medical records and the appropriate eCRF.

Reasons for treatment discontinuation should be classified as follows:

- Death
- Progressive disease
- Treatment-related toxicity
- Toxicity unrelated to treatment
- Investigator judgment
- The Investigator may withdraw a subject if, in his/her judgment, it is in the subject's best interest to do so.
- Noncompliance
- Subject voluntary withdrawal
 - A subject may withdraw from the study at any time, for any reason. If a subject discontinues treatment, an attempt should be made to obtain information regarding the reason for withdrawal.
- Early withdrawal of subject(s)
- Sponsor decision

Subjects who are unavailable for follow-up evaluations should be classified as lost to follow-up for 1 of the following reasons:

- Lost to follow-up: For a subject to be considered lost to follow-up, the investigator must make two attempts to re-establish contact with the subject. The attempts to re-establish subject contact must be documented (e.g., certified letter).
- Death: Date and cause of death will be recorded for those subjects who die within 30 days after treatment (telephone contact is acceptable).

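### The DLT window in 10.3 is tied to the final I-PDT, so read literally it drops a DLT from an earlier course; the effect is probably small, but one patient can reverse a Table 2 decision

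*Combined protocol and SAP*

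**What the plan says.** Section 10.3 makes any grade 4 or higher event at least possibly related to I-PDT a DLT, identified "by recording the occurrence of AE during the first 30 days post final I-PDT treatment". It then repeats the anchor: "Dose Limiting Toxicities will be evaluated for 30 days post final I-PDT day". Section 8.1 frames the primary safety endpoint in the same way: "recording the occurrence of AE during the first 30 days post final I-PDT day".

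Section 10.4 provides for repeat treatment: "up to three sessions of I-PDT may be performed, at the discretion of the treating physician", and "treatment sessions in this study will be conducted at least 30-days apart". The last sentence of 10.3 covers a DLT that occurs before treatment is complete: "If participants experience DLTs, further I-PDT sessions will be held until DLT resolution as well as after porfimer sodium clearance".

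Table 2 decides on the "Number of patients with DLT at a given dose level" and does not name a course. At level 1, none or one of the first three leads to three more patients at that level, two or more leads to level -1, and at most one of six gives the recommended dose.

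**The concern.** A window consisting of the first 30 days after the final treatment has an opening date as well as a closing date. With treatments at least 30 days apart, a grade 4 event soon after course 1 lies before that opening date once course 2 has been given. If course 2 is uneventful, the patient has no DLT under the literal definition, although the hold sentence has already called the event a DLT. The two parts of 10.3 do not fit together.

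The Table 2 count is the formal basis for the recommended Phase 2 irradiance and uses at most six patients per level. If the rule is left open, someone must decide after seeing the event whether it counts, and the literal answer always leans towards accepting the level.

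**Working it through.** **Does another section settle it?** Section 11.2 and Appendix D 1 (note Oi) require review of earlier adverse events before the next course. Section 17.3 collects events from the start of intervention to 30 days after the last. Section 19.6 tabulates toxicities across all cycles, and 19.7 monitors safety continuously. None says which events enter the Table 2 count.

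**Who is affected?** A patient with a related grade 4 event that resolves, who is not discontinued for "Treatment-related toxicity" (10.5), and who is then given a further, discretionary course. A DLT that ends treatment is counted, because that course is then the final one. Appendix D note 16 expects porfimer in the tumor for at least 30 days, so under the clearance condition the gap concerns mainly full later courses rather than split sessions within 14 days.

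**Reproducing the plan's figure.** Two levels × 6 patients = 12, the stated maximum (four cohorts of 3).

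**Example without any assumed rate.** Two of the first three patients have a related grade 4 event after course 1. One stops. The other resumes after resolution and clearance and completes course 2 without an event. The literal count is 1 of 3 (three more at level 1). The any-course count is 2 of 3 (go to level -1).

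**Expected size.** The documents give no DLT rate, course mix or resumption share, so all three are assumed:

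- q = DLT risk per course, constant and independent
- r = share of patients who resume after a DLT in a non-final course
- mix = percentages of patients planned for 1/2/3 courses

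Formulas for K planned courses:

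- any-course DLT: 1 − (1 − q)^K
- literal DLT: f(1) = q; f(K) = q(1 − r) + (qr + 1 − q)·f(K − 1)
- acceptance of level 1: P(Bin(6, p) ≤ 1) = (1 − p)^6 + 6p(1 − p)^5

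With q = 0.10, r = 0.2 and mix 70/20/10:

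- any-course: p = 0.7(0.100) + 0.2(0.190) + 0.1(0.271) = 0.1351, acceptance 0.811
- literal: f(2) = 0.08 + 0.92(0.10) = 0.172; f(3) = 0.08 + 0.92(0.172) = 0.2382; p = 0.7(0.100) + 0.2(0.172) + 0.1(0.2382) = 0.1282, acceptance 0.826

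| Mix (%) | q | Any-course | Literal, r = 0.1 | Literal, r = 0.2 | Literal, r = 0.5 |
|---|---|---|---|---|---|
| 70/20/10 | 0.05 | 0.941 | 0.944 | 0.947 | 0.955 |
| 70/20/10 | 0.10 | 0.811 | 0.819 | 0.826 | 0.849 |
| 70/20/10 | 0.15 | 0.658 | 0.669 | 0.681 | 0.716 |
| 85/10/5 | 0.10 | 0.850 | 0.853 | 0.857 | 0.868 |
| equal | 0.10 | 0.687 | 0.708 | 0.729 | 0.790 |

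For mix 70/20/10 and q = 0.10, the chance of an uncounted DLT per patient is the any-course p minus the literal p: 0.0034, 0.0069 and 0.0173 for r = 0.1, 0.2 and 0.5. The chance of at least one in six patients is 1 − (1 − difference)^6 = 2%, 4% and 10%.

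A simulation of 400,000 trials of the 3+3 path at this setting gave the same acceptance rates to within 0.001. No simulated trial was accepted on the any-course count and rejected on the literal one. With one course each, or r = 0, there is no difference.

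**The case against.** The strongest reply is that only one reading gives effect to every sentence of 10.3: observe through 30 days after the last I-PDT. The hold sentence has no purpose otherwise, and Table 2 speaks of patients with a DLT, whatever the course. When a grade 4 event follows course 1, that course is the latest one; the event is called a DLT and treatment is held. Losing it means removing it from the count later, and no section provides for that. Appendix D points the same way. Note 13 sets adverse event reporting at 30 days after first standard-of-care treatment, yet the table schedules adverse event assessment on the treatment day and at one week. That anchor makes sense only as an end date.

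This stands as evidence of intent, and a reader should not infer that the authors meant to discard earlier DLTs. It does not remove the defect: the definition is stated twice in words that say otherwise, while 17.3 shows that a period with both a start and an end was written out where wanted.

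It is also fair that such an event is unlikely to go unseen, given the review before each course, continuous monitoring and the all-cycle tables. A reader might infer that early-course toxicity is lost from the primary safety data. Section 19.6 does not support that; for the primary endpoint only the wording of 8.1 is too narrow.

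**Conclusion.** The concern holds as a fault in a stated rule. Applied as written, 10.3 leaves out a DLT from an earlier course when the patient is re-treated without an event, against its own hold sentence, and no other section says how Table 2 should count it.

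A reader might infer that the error can favour only level 1. That is too strong. The literal count cannot exceed an any-course count, so relative to that count it favours whichever level is under test. This is mainly level 1, because level -1 is reached only after level 1 has been rejected, but the same undercount there would favour level -1. Against a first-course-only window, the direction would not be fixed.

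A large effect is not supported either. If 10-20% of affected patients resume and most patients have one course, acceptance rises by about 0 to 2 percentage points (0.3 to 2.3 in the 70/20/10 rows). It reaches 10 points (0.687 to 0.790) only if multiple courses and resumption are both common. Calling the effect probably small is a judgement, since every input is assumed. The example shows that a single patient is nevertheless enough to reverse a decision.

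**What to change.** In 10.3 and 8.1, define the window as running from the start of study treatment through 30 days after the last I-PDT. The start can be the first porfimer administration or, at the latest, the first I-PDT. The later start also closes the gap and leaves out the roughly 48 hours before any light, when events cannot depend on irradiance. Add that a qualifying event after any course or session counts that patient once as a DLT in Table 2, regardless of later treatment.

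The cost is a few sentences. No patients, visits or data are added, because 17.3 already collects these events. There is no extra waiting, because 10.3 already evaluates DLTs to 30 days after the final I-PDT.
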